6.4 Unscheduled Visits

An unscheduled visit is defined as any healthcare visit (e.g. office visit, outpatient visit, urgent care, observational visit, ER visit, hospitalization) between scheduled follow-ups, due to a cardiovascular event.

Such visits need to be documented by completing the Health Care Utilization form.

6.5 Study Flow Chart

The Study Flow Chart (fig. 1) and Table 3 below summarize subject flow and requirements of this clinical study.

Figure 1: Study Flow Chart

[figure not shown]

Table 3: List of all clinical study specific tests/activities and procedures

Study Activity	Visit	Enrollment	Baseline Visit (Max 10 days from Informed Consent)	Procedure Visit (Max 14 days after baseline)	1-month Visit (Within 30 days post procedure)	6-month Visit (± 30 days)	12-month Visit (± 30 days)
Eligibility check		X					
Informed Consent Process		X					
Demographics			X				
Physical information			X				
Cardiac History			X				
Arrhythmia History			X				
12 Lead ECG			X				
Antiarrhythmic / Anti-coagulant Medication			X		X	X	X
EQ-5D questionnaire			X			X	X
Mapping of cardiac structures				(X)			
RF Ablation				(X)			
User Experience				(X) ¹			
Obtain Procedure USB				X			
Arrhythmia Recurrence					(X)	(X)	(X)
48-hour Holter-monitoring (AF only)							(X) ²
Healthcare Utilization information					(X)	(X)	(X)
Deviation		(X)	(X)	(X)	(X)	(X)	(X)
Withdrawal		(X)	(X)	(X)	(X)	(X)	(X)

(X) If applicable

¹ Only required for first procedure performed by physician

² Only required for patients treated for AF

6.6 Description of Activities Performed by Sponsor Representatives

Trained Sponsor personnel may perform certain activities to ensure compliance to the CIP and may provide technical expertise.

While Sponsor representatives may perform these activities, the Principal Investigator remains responsible for ensuring all clinical study data is collected as required per CIP.

Sponsor personnel will not:

- Administer the informed consent process
- Practice medicine
- Provide medical diagnosis or treatment to subjects
- Discuss a subject's condition or treatment with a subject without the approval and presence of a health care practitioner
- Independently collect study data

6.7 Subject Study Completion

Subject participation in the clinical study will conclude upon completion of the 12-Month visit and 48-hour holter monitoring (if applicable). Upon completion of subject participation in the clinical study, the subject will return to standard of care.

6.8 Subject Withdrawal

Subjects must be informed about their right to withdraw from the clinical study at any time and for any reason without sanction, penalty or loss of benefits to which the subject is otherwise entitled. Withdrawal from the clinical study will not jeopardize their future medical care or relationship with the investigator. Subjects will be requested to specify the reason for the request to withdraw. The investigator must make all reasonable efforts to retain the subject in the clinical study until completion of the clinical study.

A subject will be considered 'Lost to Follow-up' after one missed visit and a minimum of two unsuccessful phone calls from study site personnel to the subject or subject's contact to schedule the next follow-up visit. These two phone calls must be documented in the subject's hospital records. If the subject is deemed lost to follow-up, a letter should be sent to the subject's last known address or to the subject's general practitioner (GP) and a copy of the letter must be maintained in the subject's hospital records.

6.9 Study Committees

6.9.1 Publication Committee (PC)

A Publication Committee shall be established to oversee study publications. Publication Committee membership may include Principal Investigators, a representative of the Sponsor and a statistician. The Publication Committee will be responsible for identifying, selecting and approving publication proposals and determining authorship according to a Publication Plan. A Publication Committee charter will define membership of the committee and outline the roles and responsibilities of the committee, as well as rules to define authorship.

7 Statistical Considerations

The following section describes the statistical methods for the observational study and justification of the design.

7.1 Endpoints

The endpoints for evaluating the objectives are as following:

- Summary of subjects that used EnSite™ AutoMap and AutoMark module
- Summary of EnSite™ Automap and AutoMark module software settings used per arrhythmia
- Assessment of EnSite™ AutoMap Module including:
 - o Mapping time associated with (re-)mapping one or multiple arrhythmias per catheter type used in a single subject
 - o Used Points per Minute per catheter type stratified by arrhythmia type and mapping type
- Rate of acute success based on pre-defined procedural endpoints
- Freedom from arrhythmia recurrence through 12 months
- Number of repeat ablations up to 12 months
- Summary of NavX patch placement locations used
- Number of gaps in lesions identified requiring touch-up ablation
- Changes in EQ-5D quality of life score at 6 and 12 months
- Number of unscheduled visits and hospitalizations due to arrhythmia
- Overall procedure time

- Overall system stability

7.1.1 Analysis Methodology

The endpoints will be summarized descriptively based on available data or measurements in the analysis population. No hypothesis testing will be performed.

Summary of subjects that used EnSite™ AutoMap and AutoMark module:

- Overall usage of EnSite™ AutoMap Module:
This will be summarized by the number and proportion of subjects with a procedure that use EnSite™ AutoMap.
- Overall usage of AutoMark module:
This will be summarized by the number and proportion of subjects with a procedure that use AutoMark.

Summary of EnSite™ Automap and AutoMark Module software settings used per arrhythmia:

- Usage of EnSite™ AutoMap Module features:
Among the subjects with EnSite™ AutoMap module features used during the procedure, the initial settings of EnSite™ AutoMap features listed below will be summarized descriptively by each arrhythmia, as number and proportion or mean and standard deviation as appropriate.

AutoMap Settings:

- Score Threshold (%)
- Cycle length tolerance (ms)
- Speed limit (mm/s)
- Distance threshold (mm)
- Signal-to-Noise ratio (number)
- Force lower limit (grams)
- Force upper limit (grams)
- Enhanced Noise rejection enabled? (Y/N)
- Independent Scoring Interval enabled? (Y/N)

- Usage of AutoMark Module features:

Among the subjects with AutoMark features used during the procedure, the AutoMark features listed below will be summarized descriptively as number and proportion or mean and standard deviation as appropriate.

AutoMark Parameters (values and diameters of Lesion Color and Lesion Size Metrics):

- Energy (Joules)
- Time (Seconds)
- Impedance Drop (Ohms)
- Impedance Drop (%)
- Average Power (Watts)
- Maximum Power (Watts)
- Average Temperature (Degrees Celsius)
- Max. Temperature (Degrees Celsius)
- Average Force (Grams)
- Max. Force (Grams)
- *LSI (number) → OUS only*
- *FTI (gr/s) → OUS only*

AutoMark placement settings:

- AutoMark Spacing (mm)
- Min AutoMark Time (s)
- Away Time (s)

Mapping time associated with (re-)mapping one or multiple arrhythmias per catheter type used in a single subject:

- Mapping time will be summarized (e.g. as mean, median, standard deviation, minimum and maximum) across arrhythmia types and for each type of arrhythmia per catheter, as appropriate for the following map types:
 - o Manual
 - o AutoMap
 - o Combination Manual Map / AutoMap
 - o TurboMap™

Used Points per Minute per catheter type stratified by arrhythmia type and mapping type:

- Mapping points per minute used will be summarized (e.g. as mean, median, standard deviation, minimum and/or maximum) across arrhythmia types and for each type of arrhythmia per catheter as appropriate, with following map types:
 - o Manual mapping
 - o AutoMap
 - o Combination Manual Map / AutoMap
 - o TurboMap™

Rate of acute success based on pre-defined procedural endpoints (refer to Appendix C):

- The number and proportion of subjects with acute success will be summarized.

Freedom from arrhythmia recurrence: Arrhythmia recurrence is defined as documented atrial arrhythmia for 30 seconds or longer or documented ventricular arrhythmia either treated by ICD or lasting 20 seconds or longer throughout the follow-up period.

- This analysis will be performed using the Kaplan-Meier (KM) analyses. The start date is the date of the index procedure. For subjects who do not experience an event, their follow up duration will be defined from the start date to the date of death, withdrawal, or last follow-up, whichever occurred later.
- Time to arrhythmia recurrence is defined as time from index procedure to the date of the first recurrence. For subjects with AF, events occurring within the blanking period (defined as the first 90 days after the index procedure) will be excluded from the analysis.

Number of repeat ablations up to 12 months. This will be summarized as:

- Total count of repeat ablations up to 12 months among all subjects in the analysis population defined in section 7.1.3
- Total number of subjects who experience at least one repeat ablation up to 12 months among all subjects in analysis population defined in section 7.1.3

Summary of NavX Patch placement locations used

- The number and proportion of subjects with NavX patches (Surface Electrode Patches) placed by location

Number of gaps in lesions identified during the procedure that require touch-up ablation:

- The number and proportion of subjects with gaps in lesions identified will be summarized and reported.
- The summary of number of gaps identified will be reported.
- The number and proportion of subjects where the AutoMark Module assisted in identifying these gaps will be summarized and reported.

Changes in EQ-5D quality of life score at 6 and 12 months:

- Changes in EQ-5D at 6 months from baseline, and changes in EQ-5D score at 12 months from baseline will be summarized.

Number of unscheduled visits and hospitalizations due to arrhythmia:

- The number of unscheduled visits due to arrhythmia, or hospitalizations due to arrhythmia will be summarized per subject and presented as the number of subjects

Overall procedure time:

- Overall procedure time for the index procedure will be summarized e.g. as mean, standard deviation, minimum and/or maximum. Procedure time will be derived as (Procedure stop time (Last catheter out) - Procedure start time (first catheter in)).

Overall system stability:

- Proportion of subjects with the system stable throughout the procedure. System stability will be based on the opinion of the investigator.

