Sustained ventricular tachycardia (VT) and ventricular fibrillation (VF) are typically a manifestation of significant structural heart disease and often associated with a high risk of sudden cardiac death. Implantable cardioverter defibrillators (ICDs) remain the mainstay of therapy for prevention of sudden cardiac death associated with these arrhythmias. However, ICDs treat the arrhythmia after it occurs and does not prevent the arrhythmia. Recurrent ventricular arrhythmias can lead to multiple ICD shocks that are painful, decrease quality of life and cause post-traumatic stress disorder. Spontaneous VT and ICD shocks are also associated with an increased risk of death and progressive heart failure. Antiarrhythmic drugs, notably amiodarone, reduce arrhythmias for some patients, but have limited efficacy for long-term management, particularly for scar-related re-entrant arrhythmias. In addition, antiarrhythmic drugs have the potential for significant adverse effects that includes negative inotropy, pro-arrhythmia and non-cardiac organ toxicities that limit their long-term use. Catheter ablation offers an alternative therapy for preventing arrhythmias, and can be life-saving when frequent episodes (VT storm) threaten survival. (Nof, Stevenson, & John, 2013) (Pedersen, et al., 2014)

The incidence and treatment complexity of these arrhythmias represent an opportunity for the EnSite™ Velocity Cardiac Mapping System due to the increased case complexity and duration, as mapping system precision is a key requirement to maximize the success of these challenging procedures. As a result, the EnSite Precision™ System was developed to introduce features such as Delayed Enhancement Magnetic Resonance Imaging (DE-MRI) image integration, lesion marking automaticity, automatic mapping, and workflow flexibility to aid in the success of complex ablation procedures. This clinical study is intended to understand how the EnSite Precision™ System is utilized in the treatment of complex ablation procedures.

4 Devices Used

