Appendix C: Definitions

Non-study Specific Definitions

Vulnerable Subject

Vulnerable subject is defined as individual whose willingness to volunteer in a clinical investigation could be unduly influenced by the expectation, whether justified or not, of benefits associated with participation or of retaliatory response from senior members of a hierarchy in case of refusal to participate.

EXAMPLE Individuals with lack of or loss of autonomy due to immaturity or through mental disability, persons in nursing homes, children, impoverished persons, subjects in emergency situations, ethnic minority groups, homeless persons, nomads, refugees, and those incapable of giving informed consent. Other vulnerable subjects include, for example, members of a group with a hierarchical structure such as university students, subordinate hospital and laboratory personnel, employees of the Sponsor, members of the armed forces, and persons kept in detention.

Complaint

Any written, electronic or oral communication that alleges deficiencies related to the identity, quality, durability, reliability, safety, effectiveness or performance of a device after it is released for distribution.

Study Specific Definitions

Arrhythmia recurrence

For the purpose of this clinical study, recurrence of arrhythmia is deemed to have occurred only when the arrhythmia is documented on ECG or during a period of monitoring e.g. Holter-monitoring, implantable cardiac monitor, ICD, CRT... Atrial arrhythmias must be 30 seconds or longer. Ventricular arrhythmias are any treated by ICD or 20 seconds or longer.

Blanking period (AF only)

The 3-month (90 days) period of time following a procedure in which AF episodes can occur as part of the body's healing response. Any arrhythmia activity during that blanking period is not counted in the study's results and is not used in determining success or failure of the procedure.

Acute success

For the purpose of this study, acute success is attained when one (or multiple) predefined procedural endpoints, have been realized. These predefined procedural endpoints include, but are not limited to:

- Abolition of all clinical ventricular ectopies and unstable ventricular arrhythmias
- Bidirectional block across CTI
- Block across mitral isthmus
- Confirmation of vagal reflexes
- CS isolation
- Documentation of block at a critical isthmus of conduction
- Elimination and noninducibility of tachycardia following ablation
 - o With burst pacing

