 - o With Isoproterenol
 - o With programmed atrial and ventricular stimulation
- Elimination of dormant conduction
- Elimination of LAVA
- Elimination of local Purkinje potentials
- Lines connecting scar to anatomic conduction barrier
- Lines parallel to scar border zone

- Pulmonary Vein capture with exit block
- Pulmonary Vein electrical isolation
- Scar homogenization
- Superior Vena Cava isolation
- Termination of tachycardia during RF energy application

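### The 90-day blanking for subjects with AF removes ventricular as well as atrial events, and recurrence is pooled in one curve whatever arrhythmia was ablated

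*Combined protocol and SAP*

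**What the plan says.** **Event.** Section 7.1.1 counts as recurrence a "documented atrial arrhythmia for 30 seconds or longer or documented ventricular arrhythmia either treated by ICD or lasting 20 seconds or longer". Section 6.3.3 and the definition in Appendix C use the same thresholds. None of the three requires the event to be of the kind that was ablated.

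**Blanking.** Section 7.1.1 continues: "For subjects with AF, events occurring within the blanking period", set at 90 days from the index procedure, are left out. Appendix C is equally wide: "Any arrhythmia activity during that blanking period is not counted". Its reason is narrower, since it describes a "period of time following a procedure in which AF episodes can occur as part of the" body's healing response.

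**Estimator.** Section 7.1.1 names a Kaplan-Meier analysis from the index procedure to the first recurrence, without strata. Section 7.1.4 pre-specifies no subgroups. Elsewhere in 7.1.1, mapping points per minute are summarized "across arrhythmia types and for each type of arrhythmia per catheter as appropriate".

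**Population.** Both atrial and ventricular ablations are in scope. Section 3 gives AF and VT as background and says of the latter: "Catheter ablation offers an alternative therapy for preventing arrhythmias, and can be life-saving when frequent episodes (VT storm) threaten survival". The acute-success list in Appendix C includes "Abolition of all clinical ventricular ectopies and unstable ventricular arrhythmias" as well as "Pulmonary Vein electrical isolation". By arrhythmia type, section 5.4.2 excludes only patients presenting with AVNRT or AVRT alone.

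**The concern.** Two features of the rule act together.

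First, the blanking is wider than its justification. AF during healing is a reason to disregard early AF. It is not a reason to disregard a ventricular arrhythmia in the same subject, least of all one that was itself ablated.

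Second, the event is not tied to what was treated, and all subjects appear to enter one curve. New AF after a VT ablation would be called recurrence, and subjects with and without AF would have different counting windows within one estimate.

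The third objective (section 5.2) relates system usage to patient outcomes, and freedom from recurrence is one of the 12-month outcomes. What is at stake is what that estimate means. The study is descriptive and tests no hypothesis, so no error rate or power is affected.

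**Working it through.** The documents show no sample size, case mix, event rate or expected freedom from recurrence that could be reproduced, so the check is a literal reading of the rules.

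**Step 1. Scope of the blanking against its reason.** The operative terms are events (7.1.1) and any arrhythmia activity (Appendix C). Neither is limited to atrial arrhythmias. The reason in Appendix C refers to AF episodes only. Ventricular events are therefore inside the rule and outside its reason.

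**Step 2. Apply the rule to constructed cases.** These are illustrations, not frequencies. Each subject has only the event shown.

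| Subject | Event | Result as written |
|---|---|---|
| With AF; AF ablated | ICD-treated VT, day 20 | Not counted |
| With AF; AF and VT both ablated | ICD-treated VT, day 20 | Not counted |
| Without AF; VT ablated | ICD-treated VT, day 20 | Counted |
| With AF; AF ablated | ICD-treated VT, day 120 | Counted |
| VT only ablated | AF lasting 45 s, day 120 | Counted as recurrence |

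The second row is the clearest. A ventricular arrhythmia was treated and came back, yet the subject is event-free on the curve. The third row has the same event on the same day, and it counts because the subject does not have AF.

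**Step 3. Who is blanked.** Section 7.1.1 does not define subjects with AF. For the 12-month Holter, section 6.3.3.2 and footnote 2 of Table 3 refer to patients treated for AF, while the Holter paragraph that follows 6.3.3.2 uses the looser phrase for the same group. Treated for AF is therefore the likely meaning in 7.1.1, but it is not stated there. If a history of AF were enough, a subject with such a history who had only VT ablated would also lose ventricular events before day 91.

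**Step 4. What the pooled curve describes.** It is not return of the treated arrhythmia, because rows 4 and 5 count and row 2 does not. It is not freedom from any qualifying arrhythmia since the procedure, because rows 1 and 2 do not count. Literally, it is freedom from any qualifying arrhythmia after day 90 in subjects with AF and from the procedure onward in everyone else.

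**The case against.** **The rule is coherent on its own terms.** The last sentence of the working describes a target that the rule meets exactly. This stands as far as it goes. A reader might infer that the rule contradicts itself whatever is being estimated. The documents do not support that, because they name no target against which to score it. What remains is that the only reason given for blanking does not cover ventricular events.

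**Early events are not lost to the study.** This also stands, and a reader might wrongly infer otherwise. Recurrence, including ventricular recurrence, is collected at the 1-month visit (6.3.3.1). Unscheduled cardiovascular visits are documented (6.4). Arrhythmia-related visits and hospitalizations, and repeat ablations, are summarized in 7.1.1 with no blanking stated. A further ventricular event after day 90 would count on the curve. None of this repairs the recurrence endpoint itself.

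**The AF-only heading in Appendix C may restrict blanking to AF episodes.** The heading fits equally well as naming the subjects concerned, and the operative sentences say otherwise. If the narrower meaning was intended, the text should say so.

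**The absence of strata is disclosed.** Section 7.1.4 says that no subgroups are pre-specified. The endpoint list asks for a breakdown by arrhythmia for module settings and points per minute but not for recurrence, and 7.4 allows further summaries. So nothing promised is missing. The case for estimates by class rests on interpretability.

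**Unreadable text may help.** The content of 7.1.3 and Appendix G, and the CRFs, could bear on case mix or on who enters this endpoint. Their absence from view is not a defect. The visible wording of 7.1.1 and Appendix C would still need to be reconciled.

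**Conclusion.** The point holds as a minor one. As written, the blanking removes early ventricular events in subjects with AF without a stated reason, including where a ventricular arrhythmia was treated. Combined with an event rule that ignores what was ablated and a single curve without strata, this makes the 12-month estimate hard to interpret. The harm is limited to one descriptive endpoint.

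Its size cannot be derived. It depends on how many subjects with AF have a qualifying ventricular event before day 91 and none later, on how many events are of a class that was not treated, and on the case mix. If there are few of either, the curve barely changes. A reader might take 90 of 365 days as the size. That is only the length of the blanking period. It would be the same under atrial-only blanking, and it is not a share of events.

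A reader might also infer that return of isolated ectopy is missed. The documents do not show that subjects with ectopy alone are enrolled, so this is not part of the finding.

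The conclusion assumes a literal reading of 7.1.1 and Appendix C and a population that includes both atrial and ventricular ablations.

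**What to change.** 1. **Blanking.** In 7.1.1 and Appendix C, limit the 90-day analysis blanking to atrial events in subjects treated for AF at the index procedure, using the Holter wording of 6.3.3.2 and Table 3. Ventricular events then count from the index procedure in all subjects. Make the two sections agree. This concerns the analysis only.
2. **Estimates by class.** Add descriptive Kaplan-Meier estimates by the class treated at the index procedure (atrial, ventricular, both), counting events of that class with the existing thresholds. Adjust 7.1.4 to match.
3. **Pooled curve.** Keep the any-arrhythmia curve as a second summary. Its label should state that atrial events before day 91 are not counted in subjects treated for AF.

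**Cost.** The change needs a small derivation. There will be fewer subjects per curve, and the figures may be less favourable. Before adopting it, check that the CRFs record the treated arrhythmia and the type and date of each recurrence. The plan already needs arrhythmia type for the settings summaries and must identify subjects treated for AF for the Holter, so new data collection may not be needed.

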6.3.3 Scheduled Follow-ups

In-clinic follow-up visits are scheduled at 1 month, 6 months and 12 months after procedure. The scheduled visit windows are calculated from the index procedure.

6.3.3.1 1-Month Visit (within 30 days from procedure)

The 1-month visit needs to be performed within 30 days post procedure, depending on the hospital's standard practice for 1st follow-up post procedure.

The following information is collected:

- Arrhythmia recurrence
 - o For the purpose of this clinical study, recurrence of arrhythmia is deemed to have occurred only when the arrhythmia is documented on ECG or during a period of monitoring e.g. holter-monitoring or implantable cardiac monitor. Atrial arrhythmias 30 seconds or longer will be collected. Ventricular arrhythmias treated by an ICD, or lasting 20 seconds or longer will be collected.
- Antiarrhythmic / Anticoagulant medication
- Healthcare Utilization information when applicable
- Protocol deviation, when applicable

6.3.3.2 6- and 12-Month Visit (\pm 30 days)

At each visit, the following information is collected:

- Arrhythmia recurrence
 - o For the purpose of this clinical study, recurrence of arrhythmia is deemed to have occurred only when the arrhythmia is documented on ECG or during a period of monitoring e.g. Holter-monitoring or implantable cardiac monitor. Atrial arrhythmias 30 seconds or longer will be collected. Ventricular arrhythmias treated by an ICD, or lasting 20 seconds or longer will be collected.
- Antiarrhythmic / Anticoagulant medication
- Completion of the EQ-5D questionnaire

- Holter monitoring* at 12-Month visit (for patients treated for AF)
- Healthcare Utilization information when applicable
- Protocol deviation, when applicable

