***Holter Monitoring (AF only)**

Subjects with AF will be issued a holter monitor at the 12-month visit and instructed to obtain a 48-hour recording. A core laboratory will review each recording and report findings to the Sponsor.

NOTE: The Sponsor may request access to other patient data during the required protocol follow up visits or throughout the follow up period, which may include, but is not limited to, data from implanted device(s).

Record the required information on the appropriate CRF(s). Documentation of arrhythmia (e.g. ECG printouts, holter printouts, session records), where applicable, should be retrieved and submitted electronically through EDC to the Sponsor.

Sponsor representatives can be involved in providing support during the follow-up procedures.

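### For subjects who die or withdraw before 12 months, the censoring rule can count time after the last rhythm assessment as recurrence-free

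*Combined protocol and SAP*

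**What the plan says.** Section 7.1.1 analyses freedom from recurrence by Kaplan-Meier from the index procedure. For subjects without an event, "their follow up duration will be defined from the start date to the date of death, withdrawal, or last follow-up, whichever occurred later". For AF, events in the first 90 days are excluded.

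Section 6.3.3 states that "recurrence of arrhythmia is deemed to have occurred only when the arrhythmia is documented on ECG or during a period of monitoring", and Appendix C repeats this with further examples of monitoring. Visits are at 1, 6 and 12 months, the last two with a window of 30 days either side.

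Table 3 in section 6.5 lists the 12-lead ECG at baseline only and marks arrhythmia recurrence at follow-up as if applicable. The one scheduled monitoring test is the 48-hour Holter at 12 months, footnoted "Only required for patients treated for AF".

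On leaving the study, section 6.8 says "A subject will be considered 'Lost to Follow-up' after one missed visit and a minimum of two unsuccessful phone calls", but gives no date for that status. Section 9.2.1 puts deaths on the Withdrawal form. The case report forms are under separate cover (Appendix E), so a dating rule may exist there.

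Section 7.1.5 says that all available endpoint data will be used and nothing imputed. Section 7.1.1 adds: "No hypothesis testing will be performed".

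**The concern.** Kaplan-Meier assumes that a subject in the risk set would have an event recorded if one occurred. Once a subject stops attending, that is no longer assured. Death and withdrawal normally fall on or after the last follow-up, so taking the latest of the three dates selects the exit date for anyone who has one. Between the last assessment and exit, such a subject adds to the denominator but may be unable to add to the numerator, and estimated freedom drifts upward.

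No test depends on this. But in a descriptive study the estimate is the result, and section 7.2 expects the data to inform future best-practice recommendations.

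**Working it through.** **Inputs from the documents.** Visits at 1, 6 and 12 months; windows of 30 days either side for the last two; 90-day blanking for AF; time from the index procedure. The plan gives no figure for this endpoint to reproduce.

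**Assumptions.** Six months is day 180 and 12 months day 365. The hazard is constant, from day 90 in AF and from day 0 otherwise. Drop-out is unrelated to recurrence; half of drop-outs are last seen at day 30 and half at day 180. True freedom means what full scheduled follow-up would have documented. Drop-out, true freedom, exit dating and capture are varied because the documents do not give them.

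**Step 1: length of the gap.** The 6-month window closes at 180 + 30 = day 210 and the 12-month window at 365 + 30 = day 395. If exit is dated at window close, a subject last seen at day 30 gains 210 − 30 = 180 days. One last seen at the 6-month visit (days 150 to 210) gains between 395 − 210 = 185 and 395 − 150 = 245 days.

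**Step 2: upper-end bias.** Exit is dated at window close and no gap recurrence is captured. Let w be the drop-out share and S(t) true freedom. If observed subjects contribute a·S(t) to the risk set and unobserved ones a constant b, the large-sample Kaplan-Meier factor from t1 to t2 is [a·S(t2) + b] / [a·S(t1) + b].

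For AF with true freedom 65%, S(t) = 0.65^((t − 90)/275), so S(180) = 0.8685 and S(210) = 0.8286.

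| Interval (days) | a | b | Factor, w = 0.10 | Factor, w = 0.20 |
|---|---|---|---|---|
| 90-180 | 1 − w/2 | w/2 | 0.8751 | 0.8817 |
| 180-210 | 1 − w | w/2 + (w/2)·S(180) | 0.9590 | 0.9638 |
| 210-365 | 1 − w | (w/2)·S(180) | 0.7963 | 0.8094 |
| Product | | | 0.668 | 0.688 |

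Against a true 0.650, the bias is +1.8 points at 10% drop-out and +3.8 at 20%.

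**Step 3: range.** Bias in percentage points:

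| Case | True freedom | 6% drop-out | 10% | 20% |
|---|---|---|---|---|
| AF, upper end | 50% | +1.5 | +2.5 | +5.1 |
| AF, upper end | 65% | +1.1 | +1.8 | +3.8 |
| AF, upper end | 80% | +0.6 | +1.1 | +2.2 |
| Non-AF, upper end | 50% | +1.3 | +2.1 | +4.4 |
| Non-AF, upper end | 65% | +1.0 | +1.6 | +3.3 |
| Non-AF, upper end | 80% | +0.6 | +1.0 | +2.0 |
| AF, half of gap recurrences captured | 65% | +0.5 | +0.9 | +1.9 |
| AF, uniform withdrawal dates, no capture | 65% | +0.4 to +0.5 | +0.7 to +0.9 | +1.5 to +1.9 |
| Full capture, or withdrawal dated at last assessment | any | 0 | 0 | 0 |

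A separate simulation without blanking (400,000 subjects, 10% drop-out, same upper-end conditions) agrees. For true freedom of 80%, 70% and 60%, the written rule gives 81.0%, 71.5% and 61.9%; censoring at the last assessment gives 80.0%, 70.1% and 60.1%.

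**Step 4: the fix under the same model** (AF, true 65%, 20% drop-out). The main estimate censors event-free subjects at the last assessment and keeps all documented recurrences; here recurrence itself prompts any later contact. The sensitivity estimate carries drop-outs to withdrawal at window close.

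| Gap recurrences captured | Main estimate | Sensitivity estimate |
|---|---|---|
| None | 0 | +3.8 |
| Half | −1.6 | +1.9 |
| All | −3.1 | 0 |

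In each row the pair encloses the true value.

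**The case against.** The strongest reply is that the interval after the last visit is not necessarily unobserved. Section 6.4 requires documentation of any healthcare visit "between scheduled follow-ups, due to a cardiovascular event", and section 6.3.3 lets the sponsor request implanted-device data. With full capture the written rule is unbiased, while censoring at the last assessment can run low. This stands: it is why the range starts at zero, and why a second estimate is needed.

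The size is also uncertain. Section 7.1.1 names withdrawal, not loss to follow-up. A lost subject with no withdrawal date is censored at last follow-up, and the rule then does no harm. The endpoint is one of about a dozen descriptive summaries. All this limits the weight of the point; it does not make the latest of three undefined dates a sound censoring rule.

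Three stronger readings are tempting, and the documents do not support them:

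- A reader might infer that the rule inflates the estimate throughout. It does not touch subjects who complete the 12-month visit.
- A reader might infer that every lost subject carries about six months of false event-free time. That needs a withdrawal date at window close, and section 6.8 gives none.
- A reader might infer that, for symmetry, recurrences found after the last scheduled visit should be dropped. That conflicts with section 7.1.5. Section 3 also links ventricular tachycardia and ICD shocks to death, so such events may precede exit. For non-AF subjects with true freedom 65% and all recurrences documented, suppose 5%, 10% or 20% of recurrences are followed by exit before the next scheduled visit. Dropping them overstates freedom by about 1.3, 2.7 and 5.5 points; the written rule is then off by about 0.

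**Conclusion.** The point holds in a limited form. As written, the rule can credit subjects who die or withdraw before 12 months with recurrence-free time after their last rhythm assessment, and no readable section prevents it.

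At an assumed 6-10% drop-out, the overstatement is 0 to about 2.5 points. About 5 points needs 20% drop-out, true freedom near 50%, exit dated at window close and no capture, all together; the documents establish none of these. Every figure also assumes that drop-out is unrelated to recurrence. What is at stake is the accuracy of a descriptive 12-month figure; no test or decision rule depends on it.

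**What to change.** In section 7.1.1, replace the later-of-three-dates clause with: *Subjects without an event are censored at the last date on which arrhythmia status was assessed (scheduled or unscheduled contact, Holter or device data), and no later than death or withdrawal.* Then:

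- Define last follow-up accordingly, and say what counts as assessed. Table 3 requires no rhythm test at 1 or 6 months, and none at any follow-up visit outside AF, so the definition must rest on arrhythmia status having been recorded.
- State how the withdrawal date is set, including for subjects lost to follow-up.
- Keep all documented recurrences in the main estimate, as section 7.1.5 implies.
- As a sensitivity estimate, censor event-free subjects at the earliest of death, withdrawal or end of 12-month follow-up. The main estimate can run low and this one high, so together they bracket the answer if drop-out is unrelated to recurrence.

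Swapping later for earlier is not enough unless last follow-up is defined as an assessment of arrhythmia status.

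The cost is a few sentences, a small derivation change and one extra estimate, with no new data or tests. Reported freedom may be slightly lower. Because section 6.4 records unscheduled visits only for cardiovascular events, recurrence may itself prompt contact. The main estimate could then run low by about 1.6 to 3.1 points at 20% drop-out with half to all gap recurrences captured (AF, true 65%).
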